Procedures/assessments	Phase 0: Screening and randomization		Phase 1: Lifestyle + NB with vs without VLCKD							Phase 2: Lifestyle + NB (all participants)				Follow-up (all participants)		
	Screening (In-clinic)	Randomization (in-clinic)	Remote	Remote	Remote	Remote	Remote	Remote	In-clinic (study specific)	Remote	Remote	In-clinic (Routine)	Remote	Remote	In-clinic (study specific)	In-clinic (routine)
Visit	V1	V2	V3	V4	V5	V6	V7	V8	V9	V10	V11	V12	V13	V14	V15	V16
Timing of visits (weeks)		Start	Start	W3	W4	W6	W8	W10	W10	W12	W16	W16	W20	W26	W26	W52
Visit window (days)									±30			±30			±30	±30
Lifestyle program			X		X		X			X	X		X	X		
Naltrexone/bupropion (NB)		X							X			X			X	X
VLCKD			(X) ¹	(X) ¹	(X) ¹	(X) ¹	(X) ¹	(X) ¹								
Screening assessments and randomization																
Informed consent	X ²															
Inclusion/exclusion criteria	X	X														
Randomization		X														
Anthropometric data (height, weight, waist circumference)		X							X			X			X	X

Clinical examination (Blood pressure, heart and lung auscultation, abdominal palpitation and percussion)		X							X			X				X	X
Laboratory tests																	
Fasting glucose		X							X			X				X	X
Hemoglobin A1c		X										X					X
Lipids: LDL-cholesterol, HDL-cholesterol, triglycerides		X							X			X				X	X
Liver test: AST, ALT, gamma-GT, alkaline phosphatase, total bilirubin, albumin		X										X					X
Kidney function: creatinine, eGFR		X										X					X
Thyroid function: TSH, free T4		X										X					X
Uric acid		X										X					X
Questionnaires																	
The PsyEndoAUDIT questionnaire ³		X							X			X				X	X
The PsyEndoCIDI questionnaire ³		X							X			X				X	X
The PsyEndoEDE questionnaire ³		X							X			X				X	X
The PsyEndoHADS questionnaire ³		X							X			X				X	X
Nederlandse vragenlijst voor eetgedrag ³		X							X			X				X	X
The ObesitasIPAQ questionnaire ³		X							X			X				X	X

The quality of life (SF-36) questionnaire ³		X							X				X			X	X
The outtake questionnaire															X		
Reason for discontinuation		X							X			X			X	X	
(Serious) Adverse event (S)(AE) assessment		X							X			X			X	X	

- Depending on randomization in either intervention (with VLCKD) or comparator group (without VLCKD).
- Informed Consent must be obtained prior to performing any other Trial-related procedures as part of the standard of care.
- See appendix 4 for the respective questionnaires.

I Background and Rationale

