2.3 Secondary Endpoints

- A weight loss percentage at 10 weeks, 16 weeks and at end of trial (= 52 weeks from start)
- A proportion of patients with a weight loss percentage of 5% or more at 10, 16, 26 and 52 weeks
- A proportion of patients with a weight loss percentage of 10% or more at 10, 16, 26 and 52 weeks
- The time to reach a weight loss percentage of 5% and 10%
- The dose of naltrexone/bupropion used at 10, 16, 26 and 52 weeks and at the end of the trial
- The tolerability of VLCKD and NB
- Adherence to VLCKD and NB
- The Patient-Reported Outcome Measures (PROMs) of hunger and cravings at 0, 4, 10, 16, 26 and 52 weeks
- The change in fasting glucose, lipids and blood pressure at 10, 16, 26 and 52 weeks]

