2.4 Study design

This is a parallel multicentric longitudinal randomized controlled trial in which prospective data will be collected from the electronic health record. The inclusion and exclusion criteria will be checked and afterwards patients will be randomized to (unblinded) medication only or combination with VLCKD. Both groups include NB and lifestyle changes for 26 weeks but the patients belonging to the experimental group must follow a VLCKD in the first 10 weeks on top of it. Like the other group, the remaining 16 weeks will consist of NB combined with lifestyle interventions. Afterwards there is a follow-up extension of 26 weeks. See appendix 4 for detailed overview of clinical and biochemical parameters to be collected during the trial.

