2.5 Expected duration of the Study

[This trial will have a duration of 2 years in total. 1 year is taken into account to include the patients into the study according to the inclusion and exclusion criteria. Afterwards patients will be randomly inserted into the comparator arm (NB + lifestyle interventions) or experimental arm (NB + Lifestyle interventions + VLCKD). Both arms of the study design will be evaluated for 52 weeks. 26 weeks will consist of the treatment after which another 26 weeks will be used as a follow-up extension.]

The End of Study is defined as Last Patient Last Visit (LPLV). The CI shall notify the EC of the end of the Study. The CI will submit a final report with the results of the study, including any publications/abstracts, to the EC within 1 year of study termination.

The Sponsor or EC can decide to halt or prematurely terminate the Study when new information becomes available whereby the rights, safety and well-being of Study participants can no longer be assured, when the integrity of the Study has been compromised, or when the scientific value of the Study becomes obsolete and/or unjustifiable]

3 Study Population / Eligibility Criteria

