4.7 Naltrexone/bupropion

After starting the treatment, the dose should be increased over a 4-week period as follows:

- Week 1: One tablet in the morning
- Week 2: One tablet in the morning and one tablet in the evening
- Week 3: Two tablets in the morning and one tablet in the evening
- Week 4 and onward: Two tablets in the morning and two tablets in the evening

The maximum recommended daily dose of Mysimba is two tablets twice daily with a total dose of 32 mg of naltrexone hydrochloride and 360 mg of bupropion hydrochloride. Patients with too many side effects at high dose may return to the previous dose and continue with it (maximum tolerated dose).

Naltrexone/bupropion need to be taken orally. The tablets should be swallowed whole with some water. The tablets should preferably be taken with some food. The tablets must not be cut, chewed or crushed.

The formulation of naltrexone/bupropion exists of the following:

- Tablet core: cysteine hydrochloride, microcrystalline cellulose, hydroxypropyl cellulose, magnesium stearate, lactose anhydrous, lactose monohydrate, crospovidone type A, indigo carmine aluminium paint (E132), hypromellose, disodium edetate, colloidal silicon dioxide
- Film coating: titanium dioxide (E171), macrogol (3350), talc, indigo carmine aluminium paint (E132)

The package size consists of 112 tablets naltrexone/bupropion.]

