5.1.3.2 Timelines for reporting

- After informed consent has been obtained and after initiation of study-related interventions:
 - All AEs and SAEs will be reported in a “written diary” in between visits during the first 12 weeks after initiation of the study-related interventions.
 - After 12 weeks until the last follow-up visit, only SAEs causally related to a study-specific intervention will be reported.

All SAEs as defined in the protocol must be reported to the Sponsor within 24 hours of the study staff becoming aware of the event. The immediate report shall be followed by detailed, written reports. The immediate and follow-up reports shall identify subjects by Study identification.

SAE details will be reported by the Investigator to the Sponsor:

- By completing the SAE form in the (e)CRF

If an authorised Investigator from the reporting site is unavailable, initial reports without causality and expectedness assessment should be submitted to the Sponsor by a healthcare professional within 24 hours

of becoming aware of the SAE, but must be followed-up by medical assessment as soon as possible thereafter.

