5.1.4 Reporting requirements to Ethics Committee's (EC's)

The Investigator is responsible for ensuring that all safety events are recorded in the (e)CRF and reported to the Sponsor in accordance with instructions provided below.

The Sponsor will promptly evaluate all SAEs against medical experience to identify and expeditiously communicate possible new safety findings to Investigators and to EC('s) based on applicable legislation.

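### Section 5.1.3.2 stops reporting of non-serious adverse events at week 12, in conflict with the flowchart and the rest of section 5.1, so it is unsettled whether naltrexone/bupropion tolerability is captured in weeks 12 to 26

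*Protocol*

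**What the plan says.** Section 5.1.3.2 of the protocol divides the trial at week 12. Up to then, all AEs and serious AEs (SAEs) go into a written diary "in between visits during the first 12 weeks after initiation of the study-related interventions". The next bullet reads: "After 12 weeks until the last follow-up visit, only SAEs causally related to a study-specific intervention will be reported". No reason is given for choosing week 12.

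The treatment period is longer. Section 2.4 states: "Both groups include NB and lifestyle changes for 26 weeks". Section 2.5 confirms it: "26 weeks will consist of the treatment after which another 26 weeks will be used as a follow-up extension". Section 2.3 lists "The tolerability of VLCKD and NB" among the secondary endpoints without a time limit, and also lists the NB dose in use at weeks 10, 16, 26 and 52. Section 6.2 makes the tolerability analysis descriptive.

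Other parts of the safety plan carry no week-12 limit. Section 5.1.4 says: "The Investigator is responsible for ensuring that all safety events are recorded in the (e)CRF and reported to the Sponsor". It refers to the instructions that follow it, which are the table in section 5.1.4.2.

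**The concern.** Twelve weeks covers the 10-week diet and the 4-week NB titration, but less than half of the NB treatment period. A site that treats section 5.1.3.2 as the controlling rule would ask about AEs at weeks 16, 26 and 52, as the flowchart requires, and report none of the non-serious ones it found.

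The tolerability endpoint is most exposed. A descriptive summary depends entirely on which events were collected and for how long. Section 4.7 links dose reduction to side effects, so NB dose at weeks 16 and 26 would be reported without the AE records that explain it. Section 1 names anxiety and agitation among the common events with NB. Section 5.1.2 does not exempt them, so they are reportable until week 12 and then drop out under section 5.1.3.2.

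There are two centres, and section 7.3 dispenses with independent monitoring. If one centre follows section 5.1.3.2 and the other follows sections 5.1.3 and 5.1.4, AE counts after week 12 would partly reflect site practice, and the protocol has no independent check that would reveal it.

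**Working it through.** The protocol states no figure on this point to reproduce. The check sets the rules side by side and then measures the period in dispute.

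**Rules for non-serious AEs after week 12**

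| Place in protocol | Rule | Week-12 limit? |
|---|---|---|
| 5.1.3.2 Timelines for reporting | Only causally related SAEs are reported | Yes |
| Study flowchart | (S)AE assessment at start and weeks 10, 16, 26 and 52 (read by column position) | No |
| 5.1.3 Recording and reporting | AEs sought at each contact; all events into the medical record and eCRF | No |
| 5.1.3.3 Follow-up | Non-serious AEs followed to the patient's last visit | No |
| 5.1.4 | All safety events into the eCRF and to the sponsor | No |
| 5.1.4.2 Overview table | AE form to the sponsor within 7 calendar days | No |

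Section 5.1.3 can be squared with section 5.1.3.2 if recording and reporting are separate acts: late events would be entered but not reported. That reading does not rescue sections 5.1.4 and 5.1.4.2, which are about reporting to the sponsor. The 5.1.4.2 table allows protocol-defined exceptions in its SAE row but none in its AE row.

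**Rules for SAEs after week 12**

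- The quoted sentence limits reporting to causally related SAEs.
- A later sentence in the same section puts every protocol-defined SAE on a 24-hour clock, with no limit on time or causality.
- Section 5.1.3.5 requires all deaths to be reported whatever their cause.
- The limiting phrase refers to a study-specific intervention, which is not defined. Section 4.5 calls the intake, week-16 and week-52 visits routine for NB, so it is unclear whether an NB-related SAE counts.

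**Size of the period**

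Inputs: cut-off at week 12 (5.1.3.2), NB treatment of 26 weeks (2.4), total follow-up of 52 weeks (2.5).

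- Treatment weeks after the cut-off: 26 − 12 = 14; 14/26 = 53.8%.
- Study weeks after the cut-off: 52 − 12 = 40; 40/52 = 76.9%.
- Post-baseline AE assessments in the flowchart: weeks 10, 16, 26 and 52. Three of the four fall after week 12, two of them (weeks 16 and 26) within the treatment period.

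**The case against.** A reader might infer that late NB tolerability data are lost. The documents do not support that. Section 5.1.3 has no time limit and requires all events to be entered in the eCRF at every contact. Section 5.1.3.2 is headed as a rule on reporting, and section 5.1.2 shows that the protocol does distinguish recording from reporting. Loss follows only if section 5.1.3.2 overrides section 5.1.3, or if a site reads reported as recorded. Other late data also remain: blood pressure at weeks 16, 26 and 52 is examined and is a secondary endpoint, NB dose is an endpoint, and the flowchart collects reasons for discontinuation. This part of the objection stands. Dose and reason for discontinuation do not, however, supply the description, dates, severity and causality that section 5.1.3 requires for each AE.

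Part of the apparent harm has another cause. Section 5.1.2 removes gastrointestinal events, headache and insomnia from AE reporting for the whole trial and keeps them in the medical notes. Section 1 lists these among the most common NB events. They are no more reportable in week 2 than in week 20, and a longer window would recover none of them. This also stands: it is a separate gap.

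The sponsor can add that NB is an approved product used in both arms, that the randomised element lasts 10 weeks, that tolerability is only described, and that section 7.3 judges the risk minimal. These are reasons why a shorter window might be chosen. They do not explain why five other places in the protocol set no such limit. The 77% figure should carry little weight, because 26 of those 40 weeks are the follow-up extension.

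**Conclusion.** The contradiction is real and should be corrected. Section 5.1.3.2 ends reporting of non-serious AEs at week 12; the flowchart and sections 5.1.3, 5.1.3.3, 5.1.4 and 5.1.4.2 do not. The relevant size is 14 of 26 NB treatment weeks (54%), which contain two scheduled AE assessments. Over that stretch, non-serious AEs may be omitted, or captured differently at the two centres, if section 5.1.3.2 is taken to govern. That is a plausible choice for a site, since it is the section on timelines and the only one that states a cut-off. The consequence is an incomplete or unevenly collected tolerability endpoint, not a certain loss of data. The primary endpoint is unaffected.

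This rests on two assumptions: that the flowchart marks are correctly read by column position, and that NB treatment lasts 26 weeks. The flowchart also marks NB at week 52, and section 2.3 measures dose then, so exposure may run longer for some patients. The documents do not settle this.

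**What to change.** State one AE collection window that covers the NB treatment period, in the same terms in the flowchart and in sections 5.1.3, 5.1.3.2, 5.1.3.3, 5.1.4 and 5.1.4.2. AEs elicited at the week-16 and week-26 visits, and at week 52 if NB is still taken, would then be entered in the eCRF. If diary burden was the reason for week 12, keep that limit for the written diary alone.

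In the same edit, reconcile the SAE sentences within section 5.1.3.2 with each other and with section 5.1.3.5, and define what counts as a study-specific intervention.

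The cost is protocol wording and some data entry at visits that already include an AE assessment: at most 62 × 2 = 124 patient visits for weeks 16 and 26, or 62 × 3 = 186 with week 52, before drop-out. No visit is added and no treatment rule changes. The edit does not recover the events exempted by section 5.1.2, so any tolerability report should say that those were not collected as AEs.

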5.1.3.3 Follow-up

The Investigator must record follow-up information by updating the medical records and the appropriate forms in the (e)CRF. The worst case severity and seriousness of an event must be kept throughout the study.

SAE follow-up information should only include new (e.g. corrections or additional) information and must be reported within 24 hours of the Investigator's first knowledge of the information. This is also the case for previously non-serious AEs which subsequently become SAEs.

- All SAEs must be followed up until the outcome of the event is 'recovered', 'recovered with sequelae', 'not recovered' (in case of death due to another cause) or 'death' (due to the SAE) and until all related queries have been resolved, or until end of study (whichever occurs first).
- Non-serious AEs must be followed up until the patient's last study visit, and until all related queries have been resolved.

SAEs after the end of the study: If the Investigator becomes aware of an SAE with suspected causal relationship to the study-related interventions after the subject has ended the study, the Investigator should report this SAE within the same timelines as for SAEs during the study.

5.1.3.4 Pregnancy

Female subjects must be instructed to notify the Investigator immediately if they become pregnant during the study. The Investigator must report any pregnancy in subjects during the study to the Sponsor.

5.1.3.5 Death

All deaths will be reported without delay to the Sponsor (irrespective of whether the death is related to disease progression, study procedure or is an unrelated event). The sponsor will notify all deaths, as soon as possible after becoming aware, to the Central EC and the EC of the concerned site and provide additional information if requested.

5.1.4 Reporting requirements to Ethics Committee's (EC's)

The Investigator is responsible for ensuring that all safety events are recorded in the (e)CRF and reported to the Sponsor in accordance with instructions provided below.

The Sponsor will promptly evaluate all SAEs against medical experience to identify and expeditiously communicate possible new safety findings to Investigators and to EC('s) based on applicable legislation.

5.1.4.1 Annual reporting

The sponsor has the obligation to, once a year throughout the study (or on request), submit a progress report to the EC's containing an overview of all SARs occurred during the reporting period and taking into account all new available safety information received during the reporting period.

5.1.4.2 Overview reporting requirements

	WHAT	HOW	TO	TIMELINES
Investigator	AE	AE form	sponsor	Within 7 calendar days
	SAE	SAE form	sponsor	Immediately (within 24 hours of becoming aware of the event) Exceptions: as defined in protocol
	death	SAE form	sponsor	asap
Sponsor	death	SAE form + narrative	Ethics Committees	asap
	Annual Progress Report	APR template	Ethics Committees	annually

5.1.5 Pharmacovigilance

Any adverse reactions related to the medicinal products used by the participants in the study, can be reported to the Marketing Authorisation Holder and/or the Competent Authorities according to the pharmacovigilance guidelines.

6 Statistics and Data Analysis

Statistical analysis will be performed in accordance with ICH E9; a detailed description of the analysis is provided in the Trial-specific Statistical Analysis Plan (SAP). ICH E3 and E8 will guide the structure and content of the clinical trial report.

[The hypothesis for this trial is that the percentage of weight loss will be greater for the experimental arm than the comparator arm.]

6.1 Sample Size Determination

The sample size was determined for a two-sided two-sample t-test to test the difference in mean weight loss percentage between both treatment arms, assuming a mean weight loss of 6.75% (SD 7.12%) [unpublished, own retrospective data] in the control arm and a mean weight loss of 12% (SD 5.3) [unpublished, data provided by Pro Well] in the intervention arm. Assuming a 20% drop-out rate, a 5% significance level and 80% of power, a total sample size of 62 patients is indicated, or 31 patients per study arm

6.2 Statistical Analysis

[The primary analysis will be performed using a two-sample two-sided t-test to test the difference in mean weight loss percentage between both treatment arms. Mean weight loss percentages and the mean difference in weight loss percentage will be estimated and presented with 95% confidence intervals. A 5% significance level will be adopted for the primary analysis. Given the pragmatic nature of the trial, the primary analysis will be performed following the intention-to-treat (ITT) principle, in that all randomized patients will be analyzed in the study arm in which they were randomized, regardless of adherence to the therapy assigned to the patient. In presence of missing outcome data due to drop-out of patients for whom

no follow-up data were collected, the method of multiple imputation will be used. Fully conditional specification will be used to create 10 complete data sets, of which each will be analyzed and analysis results combined according to multiple imputation principles. Treatment arm and previous weight loss measures will be used as predictors in the imputation model.

A per protocol (PP) analysis will be performed as a secondary analysis, including patients adherent to the randomized treatment. Missing data will be dealt with as described above, using multiple imputation.

Linear mixed models for longitudinal data will be used for the analysis of a treatment effect on weight loss percentage at other time points. The explanatory model will contain treatment arm, time point and the interaction thereof. A random effect for patient will be modelled to deal with data clustering. Results will be presented as mean differences per time point with 95% confidence intervals.

The treatment effect on the proportion of patients with weight loss at various time points will be analyzed using logistic regression analysis, with generalized estimating equations (GEE) to account for data clustering. The explanatory model will contain treatment arm, time point and the interaction thereof. Results will be presented as odds ratios per time point with 95% confidence intervals

The treatment effect on the time to reach a pre-defined weight loss percentage will be analyzed using a log-rank test for time-to-event outcomes. Additionally, a Cox model will be used for the estimation of the hazard ratio with 95% confidence interval.

Descriptive analyses will be used for tolerability or adherence to treatment.]

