3.1 Inclusion criteria[]

Participants eligible for inclusion in this Trial must meet **all** of the following criteria:

1. Voluntary written informed consent of the participant or their legally authorized representative has been obtained prior to any screening procedures
2. Use of highly effective methods of birth control; defined as those that, alone or in combination, result in low failure rate (i.e., less than 1% per year) when used consistently and correctly; such as implants, injectables, combined oral contraceptives, some IUDs, true sexual abstinence (i.e. refraining from heterosexual intercourse during the entire period of risk associated with the Trial treatment(s)) or commitment to a vasectomised partner.
3. [Minimum 18 years of age at the time of Informed Consent signature]
4. Underwent bariatric surgery (RYGB or SG) with weight regain $\geq 10\%$ of nadir weight
5. People without Type 2 diabetes (T2D)
 - No history, no drugs, HbA1c < 6,5% and FPG <126 mg/dl)

All participants that are considered for Trial participation, per the above criteria will be documented on the Screening Log, including Screen Failures.

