6.2.1 Efficacy Analysis

Endpoint	Statistical Analysis Methods
Primary	Two-sided two sample t-test, with analysis following the intention-to-treat principle and multiple imputation to deal with missing data.
Secondary (if applicable)	Linear mixed models for continuous and longitudinal data. Logistic regression for binary and longitudinal data. Log-rank test and Cox model for time-to-event data. Descriptive statistics for adherence and tolerability.

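### The primary t-test is valid and adequately powered, but prespecifying adjustment for baseline weight would be a cheap improvement, with a gain that depends on an R² the protocol does not give

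*Protocol*

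**What the plan says.** Section 6.2 fixes the primary test: "The primary analysis will be performed using a two-sample two-sided t-test to test the difference in mean weight loss percentage". The table in section 6.2.1 says the same: "Two-sided two sample t-test, with analysis following the intention-to-treat principle and multiple imputation to deal with missing data". Neither mentions a covariate. The imputation model in 6.2 uses arm and earlier weight-loss values; baseline weight, site and type of surgery are not listed.

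Section 4.3 describes 1:1 central block randomization and names no stratification factor. Section 2.4 states that treatment is unblinded.

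Three baseline facts are available for every patient:
- **Weight.** The Study Flowchart schedules "Anthropometric data (height, weight, waist circumference") at the randomization visit.
- **Type of surgery.** It is part of eligibility in section 3.1: "Underwent bariatric surgery (RYGB or SG) with weight regain" of at least 10% of nadir weight.
- **Site.** The Funding and Support section names two sites.

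The endpoint in section 2.2 is the change in weight divided by baseline weight. Section 6.1 sizes the trial for the same unadjusted test: "The sample size was determined for a two-sided two-sample t-test".

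**The concern.** In a trial of 62 patients, a baseline value that predicts the outcome can do two things if it is in the model. It reduces residual variance, and it removes from the estimate the linear effect of any chance difference between the arms in that value. As written, the primary analysis does neither, and no stratification is stated that would limit imbalance by design.

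The second benefit matters most when the report is read. If the arms happen to differ in baseline weight, someone will ask for an adjusted result. In an open trial, a covariate chosen at that stage can be challenged as post hoc. One named in the protocol cannot.

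This is not a detail left to the SAP. The protocol names the primary test twice and bases the sample size on it.

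**Working it through.** **Inputs (section 6.1).** Control arm: "assuming a mean weight loss of 6.75% (SD 7.12"%). Intervention arm: mean 12%, SD 5.3. Further: "Assuming a 20% drop-out rate, a 5% significance level and 80% of power, a total sample size of 62 patients is indicated", that is 31 per arm. The share of within-arm outcome variance explained by baseline values (R²) is not given; I assume a range of 0 to 0.20.

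**Step 1: reproduce the plan's figure.**
- Difference: 12 − 6.75 = 5.25 points.
- Pooled SD: √((7.12² + 5.3²)/2) = 6.276. Standardized difference: 5.25/6.276 = 0.836.
- Noncentral t, 24 evaluable per arm: SE = 6.276 × √(2/24) = 1.81, power 81.0%.
- 24/0.8 = 30 per arm, or 60 in total, within two patients of the stated 62.
- In the other direction, 31 × 0.8 = 24.8 evaluable per arm: SE = 1.78, 95% CI half-width 3.58 points, power 82.3%.

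The planned test therefore delivers its stated power.

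**Step 2: power with adjustment.** With N = 2 × 24.8 = 49.6 and k covariates, the variance of the arm difference is multiplied by (1 − R²) × (1 + k/(N − k − 3)), with N − 2 − k degrees of freedom. The second factor is the expected cost of chance covariate imbalance: 1 + 1/45.6 = 1.022 for k = 1, and 1 + 3/43.6 = 1.069 for k = 3.

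| Assumed R² | t-test | Baseline weight only (k = 1) | Three covariates (k = 3) |
|---|---|---|---|
| 0 | 82.3% | 81.4% | 79.6% |
| 0.05 | 82.3% | 83.3% | 81.6% |
| 0.10 | 82.3% | 85.3% | 83.6% |
| 0.20 | 82.3% | 89.1% | 87.6% |

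Power breaks even at R² of about 0.02 for one covariate and 0.07 for three. The CI half-width behaves alike. With three covariates it is 3.71 at R² = 0, 3.62 at 0.05, 3.58 at 0.07 and 3.52 at 0.10, against 3.58 for the t-test.

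**Step 3: size of chance imbalance, 31 per arm, no stratification.**
- The SD of the difference in baseline means is √(2/31) = 0.254 baseline SD. A difference of 0.25 SD or more has probability 0.32; 0.5 SD or more, 0.05.
- A two-level factor split 50/50 differs between arms by 10 percentage points or more with probability 0.31, and by 20 or more with probability 0.13.
- A 0.25 SD imbalance shifts the unadjusted estimate by √R² × 6.276 × 0.25. That is 0.35 points at R² = 0.05 and 0.70 points at R² = 0.20, against a planned difference of 5.25.

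**The case against.** The strongest objection is that nothing here is wrong. Randomization makes the t-test valid, its confidence interval already allows for chance imbalance on average, it matches the sample-size basis, and sections 6.1, 6.2 and 6.2.1 agree with each other. All of that stands.

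A reader might go further and infer that the unadjusted test gives up precision, or that adjustment would probably help. The protocol does not support either. It reports no correlation between percentage weight loss and baseline weight, site or type of surgery. The endpoint is already divided by baseline weight, which removes a proportional dependence, and what baseline weight still explains is unknown. Nothing says that the two sites or the two operations respond differently. A three-covariate model would widen the interval if R² were below about 0.07, and at R² = 0 its power falls just under the planned 80%.

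A reader might also infer that randomization is unstratified. Section 4.3 is silent on this; it does not say so. The open design has no bearing on how often chance imbalance arises, only on how credible a later choice of covariate would be.

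What survives is narrower. The protocol itself fixes the primary test, a measured baseline value goes unused in it, and naming one covariate in advance risks very little.

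**Conclusion.** This is an optional improvement, not an error. Adjusting for baseline weight alone costs about 1 point of power if baseline weight explains nothing (82.3% to 81.4%). It gains about 3 points at R² = 0.10 and about 7 at R² = 0.20. Adding site and type of surgery by default is harder to defend: the loss at R² = 0 is nearly 3 points, and the three covariates must jointly explain about 7% of the variance to break even.

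The separate benefit is that adjustment removes the linear effect of imbalance in the chosen covariate, on the order of 0.35 to 0.70 points for a 0.25 SD imbalance at R² of 0.05 to 0.20, and does so by a rule set in advance.

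The power figures rest on the means and SDs in section 6.1, 20% drop-out with 24.8 evaluable per arm, no credit for imputed outcomes, and the assumed R² values. That the plan is unadjusted is certain; the size, and even the sign, of the precision effect is not.

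**What to change.** In sections 6.2 and 6.2.1, replace the t-test as primary analysis by a linear model (ANCOVA) of week-26 percentage weight loss on arm and baseline weight, plus any factor by which randomization is in fact stratified. Fit it in each imputed data set, include the same covariates in the imputation model, and combine results as already planned. Report the adjusted mean difference with its 95% confidence interval. Keep the unadjusted t-test as a sensitivity analysis.

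State in section 4.3 whether the block schedule is stratified and, if so, by what.

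Add site or type of surgery only if the sponsor's retrospective data, cited in section 6.1 for the control arm, suggest that they are prognostic. Settle this before unblinded outcome data are analysed.

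The cost is a few sentences and one table cell, with no new data and no change to the sample size. The statistical cost is one degree of freedom and about 1 point of power at worst for baseline weight alone; each further covariate or stratification factor adds to it.
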